1 INTRODUCTION

1.1 Background

CMV is a member of the Herpesviridae family, double-stranded DNA viruses which become latent in host cells after acute infection. CMV infection is ubiquitous and evidence of sero-conversion has been found in all populations. CMV infection is usually harmless, except in the fetus and the immunocompromised host. In the immunocompromised host, primary infection, reinfection or reactivation of latent virus can cause significant morbidity and mortality. Persons undergoing a solid organ transplant (SOT) are particularly susceptible to both primary infection and reactivation of CMV as a result of the pharmacologic immunosuppression used to prevent graft rejection.

The morbidity and mortality associated with CMV infection is secondary to both the direct and the indirect effects of CMV. CMV infection can result in CMV disease, both CMV syndrome and CMV tissue-invasive disease. The highest risk of CMV disease occurs in CMV-seronegative recipients of an organ from a CMV seropositive donor.

The use of either prophylactic or preemptive anti-viral therapy (AVT) has led to a reduction of CMV disease, but late CMV disease, after therapy is discontinued remains a problem.

In addition to the direct effects of CMV infection (CMV disease) the indirect effects of CMV infection include allograft rejection, decreased graft and patient survival, and an increase in opportunistic infections [Fishman & Rubin, 2007]. The indirect effects may possibly result from alterations in the immune system after subclinical reactivation episodes or by expression of viral genes during latency [Boeckh & Geballe, 2011].

Vaccines designed to induce or enhance the adaptive immune response to CMV could reduce the risk of CMV disease, allograft rejection, graft and patient survival and opportunistic infections other than CMV. The control of CMV infection is associated with preserved CMV-specific cellular immune responses, including CD4+, CD8+, and natural killer (NK) T cells [Sylwester et al, 2005]. In addition, humoral responses have also been shown to be important in preventing viral dissemination [Griffiths et al 2011].

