2.3.3 Exploratory Efficacy Endpoints

- Number of opportunistic infections other than CMV through one year post first Study Drug injection.
- Time to first CMV viremia (defined as plasma viral load of ≥ 1000 IU/mL by central assay) through one year post study first Study Drug injection.
- Time to first adjudicated CMV disease, including CMV syndrome and CMV tissue-invasive disease, through one year post first Study Drug injection.

- Number of episodes of CMV viral load of ≥ 1000 IU/mL by central assay through one year post first Study Drug injection.
- Peak CMV viral load and area under the curve (AUC) through one year post first Study Drug injection.
- Viral load area under the curve (AUC), as a measure of “cumulative viral load” through one year post first Study Drug injection.
- Number of episodes of adjudicated CMV-associated disease, including CMV syndrome and CMV tissue-invasive disease, through one year post first Study Drug injection.
- Number of episodes of viral resistance to ganciclovir or valganciclovir through one year post first Study Drug injection as determined by a central laboratory assay.
- Incidence of biopsy-proven (T or B cell) rejection (BPAR)(Banff 2007 Grade ≥ 1) through one year post first Study Drug injection.
- Estimated glomerular filtration rate (eGFR) at the last study visit calculated using the 4 variable MDRD formula.
- Incidence of clinically treated acute graft rejection through one year post first Study Drug injection.
- Patient-reported outcomes through one year post first Study Drug injection.
 - EuroQol-5 dimensions 5 levels (EQ-5D)
 - Kidney Transplant Questionnaire (KTQ)
 - Short Form Health Survey version 2 (SF-12v2)
- Healthcare resource utilization through one year post first Study Drug injection.
 - Resource use will be collected including the following: hospitalizations recorded as number of days in the Intensive Care Unit, Step-down Unit, and general medical ward (including emergency room visits greater than 24 hours), also non - protocol -related physician visits and emergency room visits of less than 24 hours.

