5.3.3 Exploratory Efficacy Assessments

- Opportunistic infections as defined in Appendix 8

- CMV Plasma Viral Load by central assay
- CMV disease: CMV syndrome and CMV Tissue Invasive Disease as defined in Appendix 7
- Genotypic resistance to valganciclovir and ganciclovir
- Biopsy Proven Acute Rejection (BPAR) as defined in Appendix 6
- eGFR at the last study visit
- Clinically treated acute graft rejection

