12.8 Appendix 8: Opportunistic Infections

- Viral infections
 - HHV-1: Herpes simplex 1 (HSV 1)
 - Herpes labialis
 - HHV-2: Herpes simplex 2 (HSV 2)
 - Herpes genitalis
 - HHV-3: Varicella zoster virus (VZV)
 - Chicken Pox
 - Shingles
 - HHV-4: Epstein Barr virus
 - Mononucleosis
 - Burkitt's lymphoma
 - Nasopharyngeal carcinoma
 - Post-transplant lymphoproliferative disorder (PTLD)
 - Oral hairy leukoplakia
 - HHV-6: Human herpes virus 6
 - Roseola subitum
 - HHV-7: Human herpes virus 7
 - Roseola subitum
 - Pityriasis rosea
 - HHV-8: Human herpes virus 8
 - Kaposi's sarcoma
 - Effusion lymphoma
 - Multifocal Castleman's disease
 - Simian virus 40
 - Jacob-Creutzfeld
 - BK virus

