Appendix 8: Opportunistic Infections *continued*

- Bacterial infections
 - Legionellosis pneumophilia
 - Nocardiosis
 - Listeriosis monocytogenes
- Fungal infections
 - Aspergillus
 - Candida
 - Coccidioides
 - Cryptococcus
 - Histoplasma
 - Mucormycosis

Diagnosis of infection must be supported by appropriate laboratory tests, histopathology, serologies, radiologic findings or culture.

Dubberke ER and Brennan DC. *Core Concepts in Renal Transplantation*. Chapter 9 Infectious Complications in Renal Transplant Recipients (A. Chandraker et al. (eds)

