12.9 Appendix 9: Special Infections Related to Kidney Transplant

Epstein Barr Virus (EBV) Infection:

Active, asymptomatic EBV infection is defined by the presence of a detectable EBV viral load as measured by a nucleic acid amplification assay. Asymptomatic infection may also be identified in lymphoid rich histopathologic specimens.

EBV Disease:

EBV disease is defined by the presence of active EBV infection with symptoms or signs attributable to the virus.

BK Virus Infection:

BK virus infection (replicative infection) defined as quantitative BK viral DNA load, in blood or urine above the detection threshold for the given laboratory's assay. BK infection is classified as either BK viruria or BK viremia or both. While the presence of decoy cells in urine on cytology is suggestive of BK infection, confirmation with a specific test (e.g., PCR) is required.

BK Virus Associate Nephropathy (BKVAN):

Proven BK virus associated nephropathy is defined by evidence of BK virus infection and the presence of:

- Renal biopsy associated with:
 - an acute tubular necrosis-like picture *or*
 - interstitial nephritis mimicking acute rejection *or*
 - chronic allograft nephropathy with confirmation of the presence of BK virus by electron microscopy, immunohistochemistry or *in-situ* hybridization for BK virus. Although intra-nuclear viral inclusions are usually seen, their presence is not mandatory for a diagnosis of BKVAN.

For purposes of this study, subjects with *presumptive* BKVAN diagnosed in the presence of renal allograft dysfunction and a positive BKV DNA PCR result from blood in a subject with no viral inclusions at light microscopy and negative immunohistochemistry/*in-situ* hybridization should be classified as BK virus infection (i.e. BK viremia rather than BKVAN).

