Classifications of opportunistic infections other than CMV: Any TEAE with the following classifications will be considered and decided by the medical and safety officers of the study team before unblinding case by case if it is an opportunistic infection: (1) SOC: Renal and Urinary disorders and HLGT= Viral infectious disorders, Chlamydial Infections disorder, Mycobacterial infectious disorders, Fungal infectious disorders, Bacterial infectious disorders, Protozoal infectious disorders; (2) SOC: Renal and Urinary disorders and HLT= Genitourinary tract inflammation and infection NEC, Bladder infections and inflammations, Renal infections and inflammation, Urethral infections and inflammations.

Count episodes of the protocol defined CMV viremia:

An episode starts with CMV viral load ≥ 1000 IU/mL by central assay and ends with two consecutive CMV viral load < 1000 IU/mL by central assay separated by at least one week in time. An episode will not be counted if it starts outside the primary study Period.

The ordinal variables below assessed by the central laboratory will be compared between treatments using the stratum-adjusted Wilcoxon rank-sum test. This test is implemented in SAS Proc Freq using the CMH2 option for tests based on row mean scores and SCORES=MODRIDIT option for use of modified standardized rank score within strata:

- Peak CMV viral load
- Cumulative viral load

Calculation of cumulative viral load:

Using the linear trapezoidal rule to calculate the area under the viral load over time curve (AUC) divided by the length of time for each subject.

The eGFR and its change from baseline will be summarized by treatment at each visit and at final visit. The change from baseline to final visit will be compared using analysis of

covariance (ANCOVA) with treatment and randomization stratum as factors and baseline value as a covariate.

Calculation of eGFR:

$$186 \times \text{serum creatinine}^{-1.154} \times \text{age}^{-0.203} \times [1.212 \text{ if Black}] \times [0.742 \text{ if Female}] ,$$

where serum creatinine is in mg/dL and age in years. The value in either bracket is 1 if the stated condition is not met. If serum creatinine is in SI units (mmol/L) instead of the US units (mg/dL) then its value needs to be converted to the US units first by multiplying a factor of 1/88.4.

Data from KTQ and SF-12 will be listed without any analysis.

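### The SAP's search for opportunistic infections is limited to events coded to the renal and urinary system organ class, while the protocol defines the endpoint by a pathogen list with no organ limit

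*SAP*

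**What the plan says.** Protocol 2.3.3 lists as an exploratory endpoint "Number of opportunistic infections other than CMV through one year post first Study Drug injection". Protocol 5.3.3 says how these infections are identified: "Opportunistic infections as defined in Appendix 8". Protocol 5.5.2.2 points to the same appendix. Appendix 8 names viral, bacterial and fungal agents, for example "HHV-3: Varicella zoster virus (VZV", Listeria, Aspergillus and Cryptococcus. Its only qualifier concerns evidence: "Diagnosis of infection must be supported by appropriate laboratory tests, histopathology, serologies, radiologic findings or culture".

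SAP 7.4.3 uses a different rule. A treatment-emergent adverse event (TEAE) goes to the study's medical and safety officers, who decide individually and blinded whether it is an opportunistic infection, if it meets one of two searches. The first is "1) SOC: Renal and Urinary disorders and HLGT= Viral infectious disorders, Chlamydial Infections disorder, Mycobacterial infectious disorders, Fungal infectious disorders", followed by bacterial and protozoal groups. The second is "2) SOC: Renal and Urinary disorders and HLT= Genitourinary tract inflammation and infection NEC, Bladder infections and inflammations", followed by renal and urethral groups. The events accepted enter a Poisson regression with treatment and randomization stratum as factors and follow-up time as offset.

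SAP Appendix 4 records that opportunistic infections were taken out of the special-interest summaries in SAP 7.5.2 because this exploratory endpoint already covers them. The summaries of special transplant-related infections and of post-transplant lymphoproliferative disorder (PTLD) were removed as well.

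**The concern.** The two documents define the same endpoint differently, and the SAP version is the narrower one. The event groups in the first search are general organism classes, so the SOC condition is what restricts it to one organ system. An Appendix 8 infection coded to any other SOC is never put in front of the reviewers.

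This matters for the trial's rationale. Protocol 1.1 says "the indirect effects of CMV infection include allograft rejection, decreased graft and patient survival, and an increase in opportunistic infections", and goes on to say that a vaccine might reduce such infections. Under the SAP rule, the rate ratio labelled as opportunistic infection would describe only those events that carry a renal and urinary code. A null result could be read as no indirect benefit when most of the relevant infections might not have been counted.

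The removal of the special-interest summary adds to the problem. It was justified as redundant with this endpoint, and that justification fails if the endpoint does not capture the Appendix 8 list.

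**Working it through.** The plan gives no event rate, capture share or power for this endpoint, so there is no planned figure to reproduce. The primary sample size (64 per arm; 46% against 25%, one-sided 5%, 80% power) does reproduce, but it does not bear on this point.

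**Step 1: the definitions side by side.**

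| | Protocol 5.3.3 and Appendix 8 | SAP 7.4.3 |
|---|---|---|
| Basis | Named agents and conditions | MedDRA groups |
| Organ condition | None | Renal and urinary SOC, in both searches |
| Evidence condition | Laboratory, tissue, serology, imaging or culture support | Not stated |
| Route for events outside the search | Not applicable | None |

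The SAP paragraph does not cite Appendix 8, and no other part of the SAP widens the search. SAP 7.5.1 fixes MedDRA Version 16, but the SAP does not say whether SOC means the primary or a secondary assignment. The yield of the search is therefore not determined by the text.

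**Step 2: what is on the list.**

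- Viral agents: HHV-1, 2, 3, 4, 6, 7, 8, simian virus 40 and BK = 9.
- Bacterial agents: 3. Fungal agents: 6.
- Total: 9 + 3 + 6 = 18, or 19 if the Jacob-Creutzfeld entry stands alone.
- Agents for which the protocol gives a urine or kidney-biopsy definition: 1. This is BK virus, in Appendix 9: "BK virus infection (replicative infection) defined as quantitative BK viral DNA load, in blood or urine".
- Conditions named under HHV-1, 2, 3, 4, 6, 7 and 8: 1 + 1 + 2 + 5 + 1 + 2 + 3 = 15 (14 distinct, because roseola appears twice). None is a kidney or bladder condition; one, herpes genitalis, is genital.

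These are counts of list entries. They show that the list is not a renal one; they do not estimate the share of events lost.

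**Step 3: precision under an assumed capture share.** Let the search capture a share f of true events, the same in both arms. With event counts E0 and E1, the variance of the log rate ratio is about 1/E0 + 1/E1. With capture f it becomes 1/(f·E0) + 1/(f·E1), so the standard error is multiplied by 1/sqrt(f):

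- f = 0.50: 1/sqrt(0.50) = 1.41
- f = 0.25: 1/sqrt(0.25) = 2.00
- f = 0.10: 1/sqrt(0.10) = 3.16

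**Step 4: illustration in terms of power.** Assume a true rate ratio of 0.5, equal allocation and a one-sided 5% test. With E total infections at full capture, power ≈ Φ(|ln 0.5| × sqrt(E·f/4) − 1.645).

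| E (assumed) | f = 1 | f = 0.5 | f = 0.25 | f = 0.10 |
|---|---|---|---|---|
| 30 | 0.60 | 0.38 | 0.24 | 0.15 |
| 60 | 0.85 | 0.60 | 0.38 | 0.21 |
| 90 | 0.95 | 0.75 | 0.50 | 0.27 |

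E, f and the rate ratio are all assumptions.

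**The case against.** The strongest reply concerns size. The documents give neither an event rate nor the share coded to the renal and urinary SOC. Depending on primary or secondary assignment, f could lie near 0 or well above 0.5. The list counts do not settle it: Appendix 9 defines only EBV and BK virus, so one agent in 18 reflects what that appendix covers, not where the others occur or how they are coded. This stands, and the loss has to be reported as unknown, with an assumed range.

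It can also be said that the consequences are limited. The endpoint is exploratory in a Phase 2 trial, infection data are collected regardless of coding, and every TEAE is tabulated by SOC and preferred term in each arm. This is true as well. But those tables scatter the events and do not give a grouped comparison of the Appendix 8 list.

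Blinded individual review does not repair the definition. It can discard ordinary urinary infections that the search returns, but the text gives it no way to add a missed case of shingles or cryptococcosis.

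On the smaller mismatch between SAP 6.1.3 (patients with at least one infection) and SAP 7.4.3 (number of infections), one can read 7.4.3 as summarising the first and modelling the second. That reading is reasonable, but 6.1.3 does not name the count, which is the protocol endpoint. It remains a minor point of wording.

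**Conclusion.** The concern holds. The SAP's search contradicts the protocol's definition, and following it as written would leave out of the exploratory comparison any Appendix 8 infection not coded to the renal and urinary SOC. The fault is under-capture: a listed organism that does carry such a code can still be counted. No grouped by-arm summary of the full list remains elsewhere in the SAP.

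The mismatch itself is certain from the text. Its size is not, because it depends on how events are coded. The factors of 1.4 to 3.2 rest on assumed capture shares of 0.5 to 0.10, equal in both arms. Equal capture would cost precision. If the vaccine's effect differed between infections inside and outside that SOC, the estimate would also answer a different question from the protocol's. Primary and secondary endpoints, alpha and sample size are untouched. This should be corrected, but it does not threaten the trial's main conclusion.

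**What to change.** Before unblinding, amend SAP 7.4.3 as follows:

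- Delete the renal and urinary SOC condition from both searches.
- Select candidate TEAEs from all SOCs with a prespecified preferred-term list mapped to Appendix 8, excluding CMV. Name the listed conditions that an infection grouping might not pick up, such as PTLD and Kaposi's sarcoma.
- State the MedDRA version in which the list is built.
- Keep the blinded individual review, and tie it to the Appendix 8 evidence rule.
- Align SAP 6.1.3 with 7.4.3: the number of infections as the modelled endpoint, and patients with at least one infection as a descriptive proportion.

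If the sponsor intends the narrower definition, the SAP should say so, justify it and label the endpoint accordingly; the special-interest summary could then no longer be dropped as redundant.

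The cost is SAP wording and a wider term search with some additional blinded review. No new data are needed.

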Study Objective(s): 1. To evaluate the efficacy of ASP0113 compared to placebo in reducing the incidence of CMV viremia (defined as plasma viral load ≥ 1000 IU/mL by central laboratory assay) through one year post first Study Drug injection in CMV-seronegative subjects receiving a kidney from a CMV-seropositive donor. 2. To evaluate the safety of ASP0113 in CMV-seronegative subjects receiving a kidney from a CMV-seropositive donor.	
Planned Total Number of Study Centers and Location(s): Approximately 80 sites globally Locations: Countries may include, but are not limited to: United States, Canada, Germany, Spain, France and Australia	
Study Population: CMV-seronegative subjects who have received a kidney from a living or deceased CMV-seropositive donor.	
Number of Subjects to be Enrolled / Randomized: 140 (70 per Treatment Group)	
Study Design Overview: This is a randomized, double-blind, placebo-controlled trial. 140 CMV-seronegative subjects who have received a kidney from a living or deceased CMV-seropositive donor will be randomized 30 days \pm 3 days after transplantation (Day 0) in a 1:1 ratio to ASP0113 or placebo. Prior to Randomization, subjects will be stratified by use of anti-thymocyte globulin and by receipt of a kidney from a living or deceased donor. Subjects will receive either 5 doses of ASP0113 or 5 doses of placebo on Days 30 \pm 3, 60 \pm 5, 90 \pm 5, 120 \pm 5, and 180 \pm 5 in relation to the day of transplant. Starting within 10 days of transplant, subjects will have received prophylactic valganciclovir or ganciclovir (dose per package insert) through the day of Randomization to prevent CMV disease. (The subject can miss up to two doses of valganciclovir or ganciclovir during this time period for any reason).	

Subjects will then continue to receive CMV-specific anti-viral prophylaxis (AVP) with valganciclovir or ganciclovir until 100 days post transplant. Subjects can have valganciclovir or ganciclovir interrupted, dose adjusted or replaced by other CMV-specific AVP per standard of care after the day of Randomization if renal function is compromised, there are toxicities related to the administration of the AVP, or for any other medically indicated reason.

In all subjects, plasma will be collected for central laboratory CMV viral load testing every two weeks from Day 100 through Day 200, then monthly through last study visit.

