7. Medical history must include demographics, (age, gender, race), diagnosis for renal failure, length of time on dialysis, history of prior kidney transplant, and diabetes.
8. A complete physical examination (PE) will be conducted at the Screening, Baseline and the Study Completion/Day 395 Visit (V13). At all other visits where a PE is performed (Visits 4, 6, 8, 10 and 12); symptom-directed physical examinations may be done. The evaluations conducted at each visit are to be performed by the Investigator or qualified medical personnel who routinely perform these evaluations in this patient population. Vital signs will be collected immediately prior to Study Drug injection, at 15 minutes and 60 minutes post Study Drug injection. Vital signs include blood pressure, pulse rate, respiratory rate and temperature. Height will be collected at the Screening Visit only. Weight will be collected at V1, V2 and at Study Completion/Day 395 (Visit 13). If Screening is done > 3 days prior to Randomization, the PE must be repeated at Randomization.
9. All concomitant medications and therapies administered from 14 days prior to transplant through the Study Completion Visit (Day 395/Visit 13) will be collected on the eCRF. Medications used for anesthesia during the transplant surgery will not be recorded.
10. Clinical laboratory samples will be drawn at Screening (Visit 1), before each Study Drug injection, at each follow-up time point for the injections, and at the last study visit. Clinical labs will be performed by a local laboratory and will include hematology, biochemistry, including a hepatic profile, urinalysis with microscopic evaluation and urine protein: creatinine ratio. Screening clinical labs may be re drawn once if initial results would preclude Randomization and the Investigator feels out of range results were transient. Results will be entered into the eCRF. Safety labs (hematology, biochemistry, hepatic profile, urine protein: creatinine ratio and urinalysis) drawn by Home Health Care for Investigator sites utilizing this service will be analyzed by the Central Laboratory.

11. For all females of childbearing potential, a urine pregnancy test will be performed at Screening, prior to each dose, at Visit 10, 12, and at the Study Completion/Day 395 Visit (Visit 13). All pregnancy tests will be done locally. For subjects who receive mycophenolate mofetil (MMF), additional pregnancy testing should be done in accordance with local requirements.

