12.3 Appendix 3: 4 Variable MDRD

Estimated GFR (eGFR) using Modification of Diet in Renal Disease (MDRD) formula

For creatinine in mg/dL:

$$\text{eGFR} = 186 \times \text{Serum Creatinine}^{-1.154} \times \text{Age}^{-0.203} \times [1.212 \text{ if Black}] \times [0.742 \text{ if Female}]$$

[American Journal of Kidney Diseases 2002; 39(Suppl 1): S76-S110. Vol 39, Issue 2, Supplement 1, Pages S76-S110, Feb 2002]

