6.1.3 Exploratory Efficacy Endpoints

- Number of patients with at least one opportunistic infections other than CMV
- Time to first CMV viremia (defined as plasma viral load of ≥ 1000 IU/mL by central assay) through one year post study first Study Drug injection.
- Time to first adjudicated CMV disease, including CMV syndrome and CMV tissue-invasive disease, through one year post first Study Drug injection.
- Number of episodes of CMV viral load of ≥ 1000 IU/mL by central assay through one year post first Study Drug injection.
- Peak CMV viral load through one year post first Study Drug injection.
- Viral load area under the curve (AUC) adjusted for duration through one year post first Study Drug injection.
- Number of episodes of adjudicated CMV-associated disease, including CMV syndrome and CMV tissue-invasive disease, through one year post first Study Drug injection.

- Proportion of subjects with viral resistance to ganciclovir or valganciclovir through one year post first Study Drug injection as determined by central laboratory assay.
- Proportion of subjects with biopsy-proven (T or B cell) acute rejection (BPAR) (Banff 2007 Grade \geq 1) through one year post first Study Drug injection.
- Estimated glomerular filtration rate (eGFR) at the last study visit calculated using the 4 variable MDRD formula.
- Proportion of subjects with clinically treated acute graft rejection through one year post first Study Drug injection.

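### SAP 7.4.3 labels SI creatinine as mmol/L but gives the µmol/L conversion factor, so any record held in mmol/L would yield an eGFR about 2,900 times too high

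*SAP*

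**What the plan says.** SAP 6.1.3 lists as one of eleven exploratory efficacy endpoints: "Estimated glomerular filtration rate (eGFR) at the last study visit calculated using the 4 variable MDRD formula".

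SAP 7.4.3 gives the formula with creatinine raised to the power −1.154 and fixes its units: "where serum creatinine is in mg/dL and age in years". The conversion rule names the SI unit: "If serum creatinine is in SI units (mmol/L) instead of the US units (mg/dL) then its value needs to be converted". The same sentence sets the multiplier for that unit at 1/88.4.

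Protocol Appendix 3 gives the same formula under the label "For creatinine in mg/dL" and has no SI conversion. The SAP's list of changes (Appendix 4) does not touch the point. The sentence in SAP 7.4.3 is therefore the only conversion rule a programmer has.

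SAP 7.4.3 summarises eGFR and its change from baseline at each visit and at the final visit. It compares the change to final visit between groups by ANCOVA, with treatment and randomisation stratum as factors and baseline as covariate.

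**The concern.** The factor 1/88.4 belongs to µmol/L, but the sentence names mmol/L. A programmer can follow the unit or the factor, and the results differ by three orders of magnitude in creatinine.

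SI records are plausible. Protocol Table 1 footnote 10 says "Clinical labs will be performed by a local laboratory", with home-drawn samples going to the central laboratory instead. The synopsis names possible locations as "United States, Canada, Germany, Spain, France and Australia". The SAP itself provides for SI values.

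There are two ways for the literal rule to do harm. A laboratory's values could be stored in mmol/L. Or a programmer could standardise all SI values to the unit the SAP names and then divide by 88.4. In either case the error enters mean-based analyses, and SAP 7.9.2 keeps all values in.

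**Working it through.** **Inputs.** From SAP 7.4.3: unit label mmol/L; factor 1/88.4; required unit mg/dL; formula 186 × Scr^−1.154 × age^−0.203 × [1.212 if Black] × [0.742 if female]. From outside the documents, a physical constant: the molar mass of creatinine, 113.12 g/mol (C4H7N3O, from atomic weights).

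**Step 1: does 1/88.4 reproduce?**
1 mg/dL = 10 mg/L. Then 10 / 113.12 = 0.0884 mmol/L = 88.4 µmol/L.
- From µmol/L to mg/dL: multiply by 1/88.4 = 0.01131. This is the SAP's figure.
- From mmol/L to mg/dL: multiply by 1/0.0884 = 1000/88.4 = 11.31. The SAP's figure does not reproduce for the unit it names.

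**Step 2: error in creatinine.** Take 0.0884 mmol/L, which is 1.0 mg/dL. The written rule gives 0.0884 / 88.4 = 0.001 mg/dL, which is 1000 times too low.

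**Step 3: error in eGFR.** All other terms cancel in the ratio:
(1/1000)^−1.154 = 1000^1.154 = 2,897.
The ratio is the same for every creatinine value, age, race and sex.

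**Step 4: examples.** Assumed subject: non-Black man aged 50, so eGFR = 186 × 50^−0.203 × Scr^−1.154 = 84.07 × Scr^−1.154.

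| True creatinine, mg/dL | µmol/L | mmol/L | Correct eGFR | µmol/L value × 1/88.4 | mmol/L value × 1/88.4 |
|---|---|---|---|---|---|
| 1.0 | 88.4 | 0.0884 | 84.1 | 84.1 | 243,569 |
| 1.357 | 120 | 0.120 | 59.1 | 59.1 | 171,180 |
| 1.5 | 132.6 | 0.1326 | 52.7 | 52.7 | 152,550 |
| 2.0 | 176.8 | 0.1768 | 37.8 | 37.8 | 109,454 |

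Only the last column is wrong. Multiplying the mmol/L value by 11.31 restores the correct eGFR in every row.

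**Step 5: effect on an arm mean, if one such value survived to analysis.** Assume 70 subjects in the arm, one final-visit creatinine of 0.120 mmol/L converted as written, and that subject's baseline converted correctly. The arm's mean change shifts by (171,180 − 59) / 70, or about 2,400 mL/min/1.73 m². This illustrates sensitivity; it does not predict that such a record exists.

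**The case against.** The strongest case on the other side is that this is one wrong character with little practical reach.

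- **It may not be in the signed SAP.** A µ can become an m when a document is converted between formats, and the whole point turns on that character. This is possible but not shown: other Greek letters and symbols survive in the two documents. The signed page should be checked, and if it reads µmol/L the point falls away.
- **Most SI data would be handled correctly.** A programmer with µmol/L values who applies 1/88.4 gets the right eGFR. This stands. A reader might infer that the SAP leaves µmol/L values without a rule. That is a strained reading, because the sentence addresses SI units generally and supplies the factor that fits µmol/L.
- **No mmol/L data are shown.** A reader might infer that eGFR in this trial will be wrong by about 2,900-fold, or that mixed reporting units by themselves cause the error. The documents do not support either. They show local laboratories, with several possible countries named, but give no reporting units. A mixture of mg/dL and µmol/L, each handled by its own unit, would not trigger the error.
- **Existing controls would probably catch it.** Protocol section 7 requires a review of data and outputs before database lock, and the SAP's key terms place resolution of data-review issues before hard lock. An eGFR above 100,000 is hard to miss. SAP 7.9.2 says values are not dropped as outliers; it does not bar correcting a derivation error. This stands as a limit on impact. It does not make the rule right, and neither document specifies a plausibility check for creatinine or eGFR.
- **The endpoint is exploratory.** This stands. The primary and secondary endpoints, the sample size and the futility rule do not use eGFR.

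**Conclusion.** As the text reads, the unit label and the factor in SAP 7.4.3 contradict each other, and neither Protocol Appendix 3 nor the SAP's change list resolves it. For a record held in or standardised to mmol/L and converted by the written rule, creatinine is 1000 times too low and eGFR is 2,897 times too high. Nothing changes for mg/dL records or for µmol/L records multiplied by 1/88.4.

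The most likely explanation is a mislabelled unit. The size rests only on the molar mass of creatinine and the exponent in the SAP. Whether any record is affected is unknown, because the documents give no reporting or storage unit for creatinine. Exposure is confined to the exploratory eGFR summaries and the ANCOVA on change from baseline. This is a minor correction, worth making because the sentence is an operative derivation rule.

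**What to change.** Check the signed SAP page first. If it reads mmol/L, replace the sentence with: *if creatinine is recorded in µmol/L, multiply by 1/88.4; if recorded in mmol/L, multiply by 1000/88.4 (11.31)*. Add that conversion follows the unit stored on each record and is done before eGFR is derived.

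Optionally, add a programmed check before lock that flags any converted creatinine outside a plausible mg/dL range for query.

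The cost is one sentence in the SAP and, if wanted, one programmed check. No new data are needed and no other analysis changes.
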